1 BACKGROUND INFORMATION AND RATIONALE

1.1 Introduction

The childhood obstructive sleep apnea syndrome (OSAS) is defined as a “disorder of breathing during sleep characterized by prolonged partial upper airway obstruction and/or intermittent complete obstruction (obstructive apnea) that disrupts normal ventilation during sleep and normal sleep patterns (1).” It is very common, occurring in 1-3% of otherwise healthy children (2). If untreated, it can result in significant morbidity, including cognitive deficits, behavioral abnormalities, poor growth, hypertension, cardiac hypertrophy and metabolic derangements (2).

Current treatment of childhood OSAS is primarily surgical (i.e., adenotonsillectomy, AT), with continuous positive airway pressure (CPAP) and other medical measures being used much more rarely (3). AT is efficacious but residual OSAS often remains (4, 5). Furthermore, this invasive treatment is expensive, sometimes refused by families (6), and is associated with morbidity (7). CPAP use is limited by poor adherence (8). Thus, efficacious alternative or adjunct medical treatments would be highly desirable. Several studies have suggested that NCS or leukotriene antagonists may be effective in the treatment of childhood OSAS. However, these studies have been limited by factors such as small size, lack of randomization and blinding, short-term follow-up, involvement of children with only very mild OSAS, and/or lack of stratifying for the presence of atopy. We therefore plan a randomized controlled trial evaluating the efficacy and safety of NCS vs placebo in children with mild to moderate OSAS. Our overall hypothesis is that NCS will be safe and efficacious in the treatment of mild to moderate childhood OSAS, particularly in children with asthma/atopy, but will require ongoing maintenance therapy.

1.2 Name and Description of Investigational Product or Intervention

Participants will be randomized to fluticasone nasal spray that is FDA-approved for the study age group. Fluticasone nasal spray (55 mcg [one spray] per nostril daily) is chosen as *in vitro* studies have shown that it has greater potency in reducing adenotonsillar cellular proliferation than budesonide or dexamethasone (9). The Penn Investigational Drug Service will prepare blinded nasal spray bottles with a metered pump (to deliver 55 mcg/0.1mL or placebo/0.1mL per pump) with a 30 day supply of solution per bottle.

1.3 Findings from Non-Clinical and Clinical Studies

1.3.1 Non-Clinical Studies

In vitro studies have shown increased glucocorticoid receptor expression in adenotonsillar tissue, with increased glucocorticoid receptor alpha mRNA expression and increased leukotriene cysteinyl receptors LT1-R and LT2-R in adenoid/tonsillar tissue from children with OSAS compared to those with recurrent pharyngitis (10, 11).

corticosteroids (NCS) have been shown to reduce tissue proliferation, increase apoptosis and decrease the production of tumor necrosis factor-alpha and interleukins 6 and 8 in adenotonsillar tissue (9, 12). These studies provide biologic plausibility for the use of NCS in the treatment of children with OSAS and adenotonsillar hypertrophy.

1.3.2 Clinical Studies

1.3.2.1 *Clinical Studies in Children*

Studies of NCS treatment of OSAS have been limited by small sample size, lack of placebo control, limited duration, and variability in baseline data (11, 13-16). However, these limited data suggest that there is a benefit from NCS. A very small study of oral prednisone in 9 children showed a nonsignificant improvement in OSAS (14), and most studies of NCS have shown significant effects. Only two of the NCS studies were randomized and placebo controlled, of which one study was very small. The larger study evaluated children with mild OSAS only (AHI < 7/hr). All previous studies of NCS were very short-term, although one showed persistence of effects 8 weeks after treatment (13). The current study will examine both the short-term and the long-term impact of NCS. No studies have evaluated the efficacy of NCS in the subset of children with OSAS and atopy/asthma. No studies have evaluated the side-effects of chronic NCS use in the OSAS population.

1.4 Selection of Drugs and Dosages

Fluticasone nasal spray (55 mcg [one spray] per nostril daily) will be used. This is the only form available of this non-investigational drug, and the usual clinical dosage for this age group.

1.5 Relevant Literature and Data

Need for additional therapies for childhood OSAS: AT is the primary treatment for childhood OSAS. AT is the 2nd commonest surgical procedure performed in children, with > 580,000 performed annually in the USA, predominantly for airway obstruction (17). At an estimated cost of \$5,442 each (18), the costs of surgery alone exceed \$3.2 billion a year in the USA. AT can result in significant adverse events, including pain, dehydration, hemorrhage (3% of patients), post-operative respiratory compromise (~25% of patients with OSAS (26, 27), nasopharyngeal stenosis, velopharyngeal incompetence and death (2). Although the surgery is generally effective, studies have shown that anywhere from 20-80% of children have residual OSAS post-operatively (4, 5). CPAP is typically the alternative therapy for OSAS, but adherence in children is limited, with up to a third dropping out, and the remainder wearing their equipment for only a portion of the night (8, 19, 20). Furthermore, young children with OSAS may develop midface hypoplasia from CPAP (21, 22). Thus, additional treatment options for childhood OSAS are desperately needed, with the realization that not all options will suit all patients. One such option may be NCS.

OSAS, inflammation, asthma/atopy and obesity: OSAS has been shown to be associated with inflammation in both children and adults (23, 24). For instance, C-reactive protein (CRP) is elevated in a dose-dependent manner in pediatric patients with OSAS (25, 26). Children with asthma have a high prevalence of OSAS, and children with OSAS are more likely to be asthmatic (27). Studies also suggest that children with atopy, as shown by

positive skin tests, are more likely to have histories suggestive of OSAS (28). Some studies of NCS have demonstrated residual OSAS (11, 13-16), as a result of which the American Academy of Pediatrics recommended that NCS should not be used as the primary treatment for moderate or severe OSAS. However, it is possible that specific subgroups of patients with moderate to severe OSAS, particularly atopic/asthmatic patients, may benefit more than others from NCS. This is further suggested by the large variability in patient response in some of the studies (15). It is possible that atopic patients are more NCS-responsive. Obese patients may also respond differently - possibly having a larger response as obesity is associated with inflammation, or conversely, a smaller response due to fixed structural narrowing from adipose tissue. No studies have specifically evaluated the response to NCS in atopic or obese subsets of children; or the effects of NCS on inflammation in children with OSAS; these will be assessed in the current study.

Genetic markers of NCS therapeutic response: The T_{h2} subset of CD4-positive T cells are the primary defense of the body against helminth and other large parasite infections (29). Differentiation of T_{h2} cells is promoted by various type-2 cytokines such as IL-4, IL-5, IL9 and IL-13. T_{h2} cells also promote the development of allergic inflammation. IL-4 from T_{h2} cells promotes the secretion of IgE antibodies from B cells, which then in turn promote the release of mediators of allergic inflammation, like histamine, from granulocytes such as mast cells and basophils (30, 31). IL-13 promotes asthma phenotypes like mucus production from goblets cells and hyper-responsiveness of airways (30, 31). Recently, a subtler role for T_{h2} responses in asthma has become appreciated. It has been shown that asthmatics can be divided into at least two subsets, and one of the key differentiators between these subsets is the expression of T_{h2} phenotypes in the lung (32). The authors of this study sought to quantify the effects of IL-13 in asthmatics, but the amount of IL-13 in bronchial brushings was below the level of detection. The investigators instead measured the expression of genes known to be induced by IL-13 in airways: periostin, CLCA1, and SERPINB2. ~50% of the asthmatics in the study had high expression of these 3 genes in airways, while the other 50% were indistinguishable from non-asthmatic controls with respect to expression of these genes. Asthmatics with the " T_{h2} -high" phenotype in their airways responded well to treatment with inhaled corticosteroids (fluticasone), while asthmatics with the " T_{h2} -low" phenotype largely did not respond to treatment. This demonstrates the utility of identifying distinct subsets of asthmatics before prescribing a treatment. Interestingly, a traditional marker of T_{h2} -dependent allergy, the number of allergens to which subjects developed a positive skin-prick-test, was not significantly different between T_{h2} -high and T_{h2} -low asthmatics, indicating that determining T_{h2} status in the affected tissue for a particular condition is more relevant than general measures of overall T_{h2} status. The effect of T_{h2} status will be determined in the current study. In the future, this may lead to personalized treatment of the child with OSAS.

Side-effects of NCS: Although most patients tolerate topical corticosteroids without side-effects, adverse events including growth, endocrine and ocular dysfunction may occur. GlaxoSmithKline recently released information showing that children using their brand of NCS had a slowing of growth velocity of -0.27 (95% confidence interval [CI]: -0.48 to -0.06) cm over a year (clinicaltrials.gov # NCT00570492). However, it is not known how this information relates to children with OSAS, as OSAS itself can impact growth (33). In addition, the GlaxoSmithKline study used a dose of 110 mcg/nostril daily, which is double

the recommended pediatric dose that will be used in the current study. Another study of high dose nasal fluticasone showed no growth effects at one year (34). Suppression of the hypothalamic-pituitary-adrenal (HPA) axis has been demonstrated in children receiving inhaled glucocorticoids. Most studies have evaluated adrenal insufficiency in the setting of only inhaled glucocorticoids. However, in a study of subjects with asthma, 122 of 143 subjects were on combined inhaled and nasal steroids; 6.1% had a morning cortisol < 3 µg/dL (35). The combination of nasal steroids and inhaled steroids predicted dysfunction (as defined by a metyrapone test) of the HPA axis. Adrenal crisis is rare, but has been reported with higher dose inhaled steroids (36). Inhaled steroids have been associated with an increased prevalence of cataracts (37). The propensity of topical corticosteroids to cause side-effects depends upon the dose and potency of the steroid, extent of systemic absorption, use of other medications that may interfere with catabolism, and likely underlying genetics. Thus, specific studies on the prevalence of NCS side-effects in children with OSAS are needed to determine the risk of these sequelae in this particular population. This will be performed in the current study.

1.6 Compliance Statement

This study will be conducted in full accordance all applicable Children's Hospital of Philadelphia Research Policies and Procedures and all applicable Federal and state laws and regulations including 45 CFR 46, 21 CFR Parts 50, 54, 56, 312, 314 and 812 and the Good Clinical Practice: Consolidated Guideline approved by the International Conference on Harmonisation (ICH). All episodes of noncompliance will be documented.

The investigators will perform the study in accordance with this protocol, will obtain consent and assent, and will report unanticipated problems involving risks to subjects or others in accordance with The Children's Hospital of Philadelphia IRB Policies and Procedures and all federal requirements. Collection, recording, and reporting of data will be accurate and will ensure the privacy, health, and welfare of research subjects during and after the study.

2 STUDY OBJECTIVES

The purpose of the study is to determine the efficacy of NCS vs. placebo in treating OSAS in children.

The primary objective of this study is to determine whether a 3-month course of NCS reduces the AHI in children with OSAS.

The secondary objectives are to:

- To determine which factors modify the response to NCS
- Determine the long-term effect of NCS vs. placebo in the treatment of OSAS in children
- Determine the side-effects associated with chronic NCS use in children with OSAS.

3 INVESTIGATIONAL PLAN

3.1 General Schema of Study Design

This is a randomized, parallel, double-blind, placebo-controlled study with change in AHI as the primary endpoint. A screening sleep study will be performed in participants with clinically suspected OSAS (please refer to figure 1). Those who meet polysomnographic criteria will undergo a battery of baseline testing on a separate day. Participants with the following baseline results: (i) DXA scans showing spine or whole body bone mineral density < -2.0 standard deviations using race specific curves with adjustment for height Z-score, (ii) ophthalmologic exam showing cataracts or intra-ocular pressure > 22 mm Hg on two measurements will be withdrawn from the study. All other participants will then be randomized in a 2:1 fashion to either NCS or placebo for 3 months.

3.1.1 Screening Phase

Children with OSAS will be recruited from the Sleep Center, as well as the Otolaryngology and Allergy Clinic at the Children's Hospital of Philadelphia. In addition, we will recruit from the Children's Hospital of Philadelphia primary care practices using real-time alerts in the electronic health record. This will be set up by the Pediatric Research Consortium (PeRC). Participants will be referred to the study team by their providers. The families who agree to be contacted will be called to discuss the study. Those who agree to participate in the study will be scheduled for a screening visit.

Parental/guardian permission (informed consent) and, if applicable, child assent, will be obtained prior to any study related procedures being performed.

At the end of this screening visit, a sleep study will be performed to confirm eligibility based on polysomnographic parameters.

3.1.2 Phase 1: Baseline visit & Randomization

Participants who met sleep study criteria will come back for a baseline visit that will include physical examination, cognitive and behavioral measures, knee height measurement, DXA scan (girls who are aged 10 or older and/or have attained menarche will have a urine pregnancy test before the DXA scan), phlebotomy (biomarkers, genetics, and cortisol levels), nasal swab for biomarkers and genetics, ophthalmology evaluation, OSAS symptoms questionnaires, nasal symptoms questionnaires, quality of life questionnaires and acoustic reflectance airway size measurement. Cognitive and behavioral measures will be obtained at a standardized time in the morning. The measurements of height and knee height will also be performed in the morning. Testing will be scheduled at the family's convenience, either all on one day or spread out over a few days. Participants with the following baseline results: (i) DXA scans showing spine or whole body bone mineral density < -2.0 standard deviations using race specific curves with adjustment for height Z-score, (ii) ophthalmologic exam showing cataracts or intra-ocular pressure > 22 mm Hg on two measurements will be withdrawn from the study and referred to clinical care. All other participants will then be randomized in a 2:1 fashion to either NCS or placebo for 3 months. Note that DXA results may not be available on the same day, in which case the participant

will be randomized, but will later be withdrawn from the study and referred for clinical care if the DXA results are abnormal.

3.1.3 Phase 2: 3-month visit

Participants randomized to both groups will receive monthly phone calls and come back at 3 months for a visit. Sleep study and all procedures performed at the baseline visit, except for physical examination, will be repeated at 3 months. Medication canisters will be weighed. Participants in the placebo group will then be referred to clinical care (for evaluation for further clinical treatment such as surgery if their sleep study is still abnormal, or for routine ongoing clinical surveillance if their sleep study has normalized). Children in the NCS group will be referred to clinical care if their sleep study shows severe OSAS or significant hypoxemia or hypercapnia, such that definitive treatment should not be delayed (AHI $> 30/\text{hr}$, more than 2% total sleep time with SpO₂ $<90\%$, end-tidal PCO₂ $> 60 \text{ mm Hg}$ for > 5 minutes, or pathologic arrhythmias)(4). In addition, children with (i) DXA scans showing spine or whole body bone mineral density < -2.0 standard deviations using race specific curves with adjustment for height Z-score, (ii) ophthalmologic exam showing cataracts or intra-ocular pressure $> 22 \text{ mm Hg}$ on two measurements will be withdrawn from the study and referred to clinical care. Note that DXA results may not be available on the same day, in which case the participant will be randomized, but will later be withdrawn from the study and referred for clinical care if the DXA results are abnormal.

3.1.4 Follow-up Phase

In order to determine the duration of action of NCS therapy for OSAS, children in the NCS group who did not require referral to clinical care as detailed in 3.1.2 will be further randomized to either placebo or continuation of NCS. Half of the initial NCS group will continue treatment with NCS, and the other half will be switched to placebo.

This follow-up phase will continue for 9 months. Families will be called every month to check on symptoms and side effects. In addition, participants will come at 6 and 9 months for short visits during which symptoms and medical history will be reviewed, vital signs assessed, height and weight measured, side-effects assessed and medication canisters weighed. At 12 months, participants will come back for a visit that will include a sleep study and all procedures performed at the 3 month visit. Children with persistent OSAS abnormalities and those with abnormal DXA scans, abnormal hormonal levels or ophthalmologic exam will be referred to clinical care.

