5.4 Safety Evaluation

Subject safety will be monitored by adverse events, vital signs, physical examinations (ocular health), sleep study results, laboratory data (cortisol, DHEAS, ACTH), cognitive and behavioral measures, and DXA scan results.

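### Hormone results are collected at month 3 but are missing from the rules that decide who is re-randomized, although abnormal levels lead to referral at month 12

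*Combined protocol and SAP*

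**What the plan says.** **Month 12.** Section 3.1.4 gives three safety reasons for sending a child to clinical care at the last visit, alongside persistent sleep apnea: bone density, eye findings and hormones. The wording is "Children with persistent OSAS abnormalities and those with abnormal DXA scans, abnormal hormonal levels or ophthalmologic exam will be referred to clinical care".

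**Month 3.** Section 3.1.3 has a sleep-study rule for the NCS group: "Children in the NCS group will be referred to clinical care if their sleep study shows severe OSAS or significant hypoxemia or hypercapnia" (pathologic arrhythmia is also listed). It then adds two safety rules. The first begins "In addition, children with (i) DXA scans showing spine or whole body bone mineral density" and the second is "ii) ophthalmologic exam showing cataracts or intra-ocular pressure" above a stated limit. The list ends there.

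**Re-randomization.** Sections 3.1.4 and 4.4 re-randomize the NCS children who did not need referral. For the referral criteria both cite 3.1.2, which is the baseline visit; the month-3 criteria are in 3.1.3. Section 3.2 makes the second allocation equal between NCS and placebo, and 3.1.4 sets the phase at nine months.

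**Hormones.** Section 4.3.1 lists cortisol at the month-3 visit. The abstract and 5.2.1 add DHEAS and ACTH. Section 5.4 counts "laboratory data (cortisol, DHEAS, ACTH" among the data by which safety is monitored. Section 6.2 makes adrenal suppression at 12 months a secondary endpoint.

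**The concern.** A result that has a stated consequence when study treatment ends has none at the point where a child may start nine more months of it. The protocol treats adrenal suppression as a known risk of the drug (8.11.2). Section 1.5 reports of an asthma cohort: "The combination of nasal steroids and inhaled steroids predicted dysfunction" of the adrenal axis. Children on inhaled corticosteroids can enter this trial, since such use is a stratification factor (3.2).

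What is at stake is consistent handling of a foreseeable safety finding. Two children with the same month-3 result could be managed differently, and nobody reading the protocol could say which of them was handled as planned.

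**Working it through.** The plan states no figure on this point, so the check is a comparison of the rules, followed by a rough count.

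**1. The rules side by side**

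| Finding | Baseline (3.1.2, 3.4.2) | Month 3, NCS group (3.1.3) | Month 12 (3.1.4) |
|---|---|---|---|
| Sleep study | severe disease excluded | severe findings: referral | persistent abnormality: referral |
| DXA | withdrawal | withdrawal and referral | referral |
| Eye exam | withdrawal | withdrawal and referral | referral |
| Hormones | measured, no rule | measured, no rule | measured, referral |

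Of the three safety tests that trigger referral at month 12, two also act at month 3. The third, hormones, does not. No section defines an abnormal hormone level.

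**2. Who is exposed to the gap.** Only the initial NCS group: children first allocated to placebo all leave for clinical care at month 3.

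**3. When the next test falls.** Section 4.4.1 lists no blood draw at the two interim visits, and Table 1 shows blood tests at three time points only. After month 3 the next scheduled hormone measurement is at month 12, unless the child withdraws and has the early termination visit (4.8.1).

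**4. Late results.** Section 3.1.3 covers a DXA result that arrives late: the child is randomized and withdrawn afterwards if the scan is abnormal. Section 8.11.2 explains why that delay is acceptable. Hormone results have neither a late-result rule nor such an explanation.

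**5. Other provisions.** Section 4.8 lets the investigator discontinue a child for adverse events or safety. Section 8.3 allows an abnormal laboratory finding to count as an adverse event. Under 8.11.1 the medical monitor and DSMB receive adverse events monthly, and DSMB meeting reports include laboratory analyses. None of these sets a hormone threshold or requires review before re-randomization. Treatment failure in 8.11.1 is defined by the need for sleep apnea therapy, not by endocrine findings.

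**6. Scale, by assumption.** Affected children = n × p; those allocated to continued NCS = n × p / 2. Section 6.4 gives n = 100. The documents give no p for this population. The only related figure is 6.1% with low morning cortisol in the asthma cohort of 1.5, where 122 of 143 were on combined inhaled and nasal steroids.

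- p = 1%: 100 × 0.01 = 1 child; 1 / 2 = 0.5 on continued NCS.
- p = 6.1%: 100 × 0.061 = 6.1, about 6 children; 6.1 / 2 = about 3 on continued NCS.
- p = 6.1% applied only to the 31 NCS children expected to have asthma or atopy (6.4): 31 × 0.061 = 1.9, about 2 children; 1.9 / 2 = about 1 on continued NCS. Users of inhaled steroids for asthma are a subset of those 31.

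**The case against.** The strongest reply is that the two lists do different jobs. The month-3 list decides who leaves the study; the month-12 sentence hands children over at the end. The handover is wider for sleep apnea too: any persistent abnormality leads to referral at month 12, but only severe findings do at month 3. Hormones are also missing from the baseline withdrawal rule and from exclusion criterion 3. On this view they are an outcome to be measured, and no gate was ever intended.

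Much of this stands. The month-12 sentence does not prove that a month-3 rule was intended, and the omission may be deliberate. But 5.4 also gives the hormones a monitoring role, and the protocol neither says what that role means at month 3 nor explains why DXA and eye findings act there and hormones do not. The wrong cross-reference makes the intended list harder still to identify.

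Three stronger readings are tempting, and the documents support none of them.

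- *A reader might infer that a child with an abnormal result has no protection.* Sections 4.8, 8.3 and 8.11.1 offer discretionary routes, and continued NCS is only one of two possible allocations.
- *A reader might infer that the 12-month adrenal comparison becomes hard to interpret.* A child held back before the second randomization is excluded before allocation, so the comparison between the re-randomized groups is not biased; at most the population is narrower.
- *A reader might take 6.1% as the expected rate.* It comes from a cohort mostly on combined steroids. This trial excludes endocrine disease and potent CYP3A4 inhibitors (3.4.2), and 8.11.2 describes these risks as infrequent at the study dosage.

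**Conclusion.** The point holds as a gap between sections that must be reconciled. Month-3 hormone results are collected and called safety data, yet have no stated bearing on re-randomization, while abnormal levels have a stated consequence at month 12. Followed as written, the protocol re-randomizes such a child, and stopping that depends on individual judgement.

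The number is probably small: 1 to 6 of 100 under the assumed 1% to 6.1%, with the top of that range illustrative only, and about half of them allocated to continued NCS. The count also depends on what is called abnormal, which is not defined. Neither the primary 3-month comparison nor the validity of the randomized 12-month comparison is in question. The change is worth making because the risk is one that the protocol itself names and the change is cheap.

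**What to change.** 1. Reconcile 3.1.2, 3.1.3, 3.1.4, 4.4 and 5.4. State whether month-3 hormone results are reviewed before re-randomization, or afterwards as for late DXA results; what counts as abnormal; and whether an abnormal result leads to referral. The clinical team decides the rule. If hormones are meant only as an outcome at baseline and month 3, say so and give the reason.
2. In 3.1.4 and 4.4, change the reference for the referral criteria from 3.1.2 to 3.1.3.
3. In section 6, specify the month-3 hormone value as the pre-re-randomization baseline covariate in the 12-month adrenal comparison. It precedes the second allocation, so adjusting for it is legitimate.

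The cost is amendment wording and one line of analysis plan. The blood is already drawn and the value already collected. Depending on the rule chosen, a few children might not be re-randomized, which would slightly reduce the 100 assumed for the follow-up phase.
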